5.6.1.1 Reporting Concentration below LLOQ

Plasma concentrations that are below the limit of quantification (BLQ) prior to administration of the first dose and up to the first measurable concentration will be counted as zero. Any other time points are excluded from the analysis.

If consecutive BLQ concentrations are followed by quantifiable concentrations in the terminal portion of the concentration curve, these quantifiable values are excluded from the PK analysis unless there is a scientific rationale not to do so, this will be documented.

Individual concentrations below the LLOQ of the assay will be reported as NQ (not quantifiable) with the LLOQ defined in the Tables, Listings and Graphs (TLGs), except the values precede the first measurable concentration. For descriptive statistics:

- If, at a given time point, 50% or less of the plasma concentrations are not quantifiable (NQ), the geometric mean, geometric CV, geometric SD, arithmetic mean, SD and median will be calculated by substituting the LLOQ for values which are NQ.
- If more than 50%, but not all, of the concentrations are NQ, the geometric mean, geometric CV, geometric SD, arithmetic mean and SD will be reported as not calculable (NC). The max value will be reported from the individual data, and the min and median will be set as NQ.
- If all the concentrations are NQ, the geometric mean and arithmetic mean will be reported as NQ, and the geometric CV, geometric SD and SD will be reported as NC.

The number of values below LLOQ is reported for each time point along with the total number of collected values. Given the first criterion above is met, three observations $>\text{LLOQ}$ are required as a minimum for a plasma concentration or PK parameter to be summarised. If only

Statistical Analysis Plan of PTCL (Version 3.0)

Protocol Code: DZ2019J0005 (Part B)

Date: Mar 25, 2023

one or two values above LLOQ are available, data are presented as a minimum and maximum with the other summary statistics as NC.

5.6.2 Summary of Pharmacokinetic Parameters

The derived PK parameters for AZD4205 following single dose and multiple doses will be summarized separately in PKS.

The following summary statistics will be presented for $AUC_{(0-24)}$, $AUC_{(0-t)}$, AUC_{ss} , C_{max} , $C_{ss\ max}$ and $C_{ss\ min}$:

- G_{mean} , calculated as $\exp[\mu]$, where μ is the mean of the data on a logarithmic scale)
- CV, calculated as $100\sqrt{\exp(s^2) - 1}$, where s is the standard deviation of the data on a log scale)
- Arithmetic mean calculated using untransformed data
- Standard deviation calculated using untransformed data
- Minimum
- Maximum
- Median
- Number of observations

The following summary statistics will be presented for R_{AC} and CL_{ss}/F :

- Arithmetic mean
- Standard deviation
- Minimum
- Maximum
- Median
- Number of observations

The following summary statistics will be presented for t_{max} and $t_{ss\ max}$:

- Median
- Minimum

Statistical Analysis Plan of PTCL (Version 3.0)

Protocol Code: DZ2019J0005 (Part B)

Date: Mar 25, 2023

- Maximum
- Number of observations

All individual PK parameters will be presented in the data listing.

5.7 Safety

5.7.1 Adverse Event

Summary tables of AEs will be produced in safety analysis set. Only the TEAEs will be included in the summaries.

An overview table will be created to present the number and percentage of participants with at least one of the following TEAEs, where participants with more than one TEAE in a particular category will be counted only once in that category.

- TEAE
- TEAE grade 3 or higher
- Treatment-emergent SAE (TESAE)
- TEAE with fatal outcome
- TEAE leading to treatment discontinuation
- TEAE leading to treatment interruption
- TEAE leading to treatment reduction
- Drug-related TEAE
- Drug-related TEAE grade 3 or higher
- Drug-related TESAE
- Drug-related TEAE with fatal outcome
- Drug-related TEAE leading to treatment discontinuation
- Drug-related TEAE leading to treatment interruption
- Drug-related TEAE leading to treatment reduction

The number and percentage of participants reporting each TEAE will be summarized by MedDRA SOC and PT. The following summary tables will be produced:

Statistical Analysis Plan of PTCL (Version 3.0)

Protocol Code: DZ2019J0005 (Part B)

Date: Mar 25, 2023

- TEAEs, by SOC, PT and CTCAE grade (all grades, grade ≥ 3)
- Drug-related TEAEs, by SOC, PT and CTCAE grade (all grades, grade ≥ 3)
- TEAEs, by SOC, PT and maximum CTCAE grade
- Drug-related TEAEs, by SOC, PT and maximum CTCAE grade
- TEAEs leading to dose reduction, by SOC and PT
- Drug-related TEAEs leading to dose reduction, by SOC and PT
- TEAEs leading to dose interruption, by SOC and PT
- Drug-related TEAEs leading to dose interruption, by SOC and PT
- TEAEs leading to treatment discontinuation, by SOC and PT
- Drug-related TEAEs leading to treatment discontinuation, by SOC and PT
- TESAEs, by SOC and PT
- Drug-related TESAEs, by SOC and PT
- TEAEs with fatal outcome, by SOC and PT
- Drug-related TEAEs with fatal outcome, by SOC and PT
- Common TEAEs, by SOC, PT and CTCAE grade (all grades, grade ≥ 3)
- Common drug-related TEAEs, by SOC, PT and CTCAE grade (all grades, grade ≥ 3)
- Common TEAEs with CTCAE grade ≥ 3 , by SOC and PT
- Common drug-related TEAEs with CTCAE grade ≥ 3 , by SOC and PT
- Common TESAEs, by SOC and PT
- Common drug-related TESAEs, by SOC and PT

In the above summaries, participants with more than one AE within a particular SOC are counted only once for that SOC. Similarly, participants with more than one AE within a particular PT are counted only once for that PT.

For summaries by maximum CTCAE grade, participants with multiple AEs within a particular SOC or PT will be counted under the category of their most severe AE within that SOC or PT.

Statistical Analysis Plan of PTCL (Version 3.0)

Protocol Code: DZ2019J0005 (Part B)

Date: Mar 25, 2023

If CTCAE grade is missing for a TEAE, it will be counted as a missing category in the summary tables by grade.

In all summary tables, the events will be sorted by descending frequency, at SOC and PT level respectively.

The number and percentage of participants in the safety analysis set who died, who died from first dose of study treatment until 28 days after last dose of study treatment, who died more than 28 days after last dose of study treatment as well as the reasons for death will be summarized. All deaths will be listed.

All individual AE data will be listed together, and treatment-emergence status will be flagged in the listing. In addition, corresponding listings of serious AEs (SAEs), AEs leading to dose reduction, dose interruption, treatment discontinuation and AEs resulting in death will be produced. AEs that occurred after participants received subsequent anti-cancer therapy will be flagged in the listing.

Where appropriate, AE subgroup analysis and analysis for adverse event of special interest may be performed.

5.7.2 Laboratory Data

The laboratory tests as specified in 4.3.3 will be summarized in the safety analysis set.

Quantitative laboratory data (except urinalysis) together with change from baseline will be summarized by visit using descriptive statistics, such as mean, standard deviation, median, min and max. By-visit box plots will be provided for selected laboratory tests like ALT, AST, ALP, total bilirubin, creatinine, total cholesterol, triglyceride, potassium, sodium, creatine kinase in serum chemistry, hemoglobin, platelet count, white blood cell count, lymphocytes (absolute), neutrophils (absolute) in hematology, and aPTT, INR in coagulation.

To present the status change in clinical significance from baseline to the worst case (abnormal clinically significant > abnormal not clinically significant > normal) post-baseline, shift tables will be provided for each laboratory test. Only participants with both baseline and post-baseline data non-missing will be included in the shift tables.

For the laboratory tests with applicable CTCAE criteria (details are shown in Appendix B), shift tables will be provided to show the shift from baseline CTCAE grade to the worst grade post-baseline.

The number and percentage of participants with post-baseline CTCAE grade worsened from baseline will also be reported by worsened CTCAE grade (all grades, grade ≥ 3). For selected laboratory tests, post-baseline CTCAE grade (worst case) compared to baseline will be provided by increase interval ($\geq 1, 1, 2, 3, 4$) using the number and percentage of participants.

The number and percentage of participants with post-baseline laboratory abnormalities associated with liver function will be reported according to Appendix C. A quadrant plot of the

Statistical Analysis Plan of PTCL (Version 3.0)

Protocol Code: DZ2019J0005 (Part B)

Date: Mar 25, 2023

maximum post-baseline ALT or AST (X-axis) and the maximum post-baseline total bilirubin (Y-axis) will be provided (vertical line of ALT or AST equal to 3 x upper limit of normal (ULN) and horizontal line of total bilirubin equal to 2 x ULN divide the quadrant plot into four quadrants). The upper right, upper left, and lower right quadrants of the quadrant plot represent the potential Hy's law, cholestasis, and Temple's corollary, respectively. The number and percentage of participants in the three quadrants will be reported separately.

Laboratory data will be included in the individual data listing.

5.7.3 **Electrocardiograms**

The ECG data will be summarized in the safety analysis set.

The ECG measurements and changes from baseline will be summarized by visit using standard descriptive statistics (mean, standard deviation, median, min and max).

The number and percentage of participants with abnormal ECG measurement (worst case) meeting each criterion below will be reported respectively. Only the post-baseline data will be included for analysis.

- Emerging absolute prolongation in QTcF interval (msec):
 - > 450 and ≤ 480
 - > 480 and ≤ 500
 - > 500
- Change from baseline in QTcF interval (msec):
 - increases from baseline > 30 and ≤ 60
 - increases from baseline > 60
- PR interval (msec):
 - > 220 msec and increase from baseline $> 25\%$
- QRS interval (msec):
 - > 120 msec
- Heart rate (bpm):
 - < 50 bpm and decrease from baseline $> 25\%$
 - > 100 bpm and increase from baseline $> 25\%$

All the ECG measurements and change from baseline will be listed in the individual data listing, together with the Overall ECG Interpretation.

Statistical Analysis Plan of PTCL (Version 3.0)

Protocol Code: DZ2019J0005 (Part B)

Date: Mar 25, 2023

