In part B, eligible patients must have relapsed after or been refractory/intolerant to \geq 1 (but not > 3) prior systemic therapy(ies) for PTCL and now require further treatment. In patients with CD30 positive ALCL, the prior systemic treatment should include CD30-targeting therapy (brentuximab vedotin) if the therapy is approved and available as standard therapy, unless in the judgment of the investigator such treatment was otherwise contraindicated.

- 8. Adequate bone marrow reserve and organ system functions, as outlined below:
 - Absolute neutrophil count (ANC) ≥ 1.5 × 10^9/L (≥ 0.5 × 10^9/L if documented bone marrow involvement with lymphoma) independent of growth factor support within 7 days of study entry.
 - Platelets $\geq 100 \times 10^{9}$ /L (or $\geq 50 \times 10^{9}$ /L if documented bone marrow involvement with lymphoma) independent of growth factor support or transfusion within 7 days of study entry.
 - Hemoglobin ≥ 8 g/dL
 - Total bilirubin ≤ 1.5 × ULN if no liver involvement or ≤ 3 × ULN in the presence of documented Gilbert's Syndrome (unconjugated hyperbilirubinemia) or liver involvement.

- Alanine aminotransferase (ALT) and aspartate aminotransferase (AST) \leq 2.5 \times ULN, or \leq 5 \times ULN if with document hepatic involvement with lymphoma.
- Creatinine ≤ 1.5 × ULN, OR calculated or measured creatinine clearance ≥ 50 mL/min as calculated by the Cockcroft-Gault method, or 24-hour measured urine creatinine clearance > 50 mL/min.
- 9. LVEF \geq 55% assessed by ECHO or MUGA.
- 10. Patients should have the ability and willingness to comply with the study and follow up.
- 11. Male patients with female partners of child-bearing potential should be willing to use barrier contraceptives (i.e., by use of condoms), during their participation in this study and for 6 months following the last dose of the study drug.
 - Male patients must refrain from donating sperm during their participation in the study and at least for 6 months after the last treatment. If male patients wish to father children they should be advised to arrange for freezing of sperm samples prior to the start of study treatment.

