If it is agreed that there is no explanation that would explain the ALT or AST and TBL elevations other than the IMP:

- Report an SAE (report term 'Hy's Law') according to Sponsor standard processes.
- The 'Medically Important' serious criterion should be used if no other serious criteria apply.
- As there is no alternative explanation for the HL case, a causality assessment of 'related' should be assigned.

If, there is an unavoidable delay, of over 3 weeks, in obtaining the information necessary to assess whether or not the case meets the criteria for HL, then it is assumed that there is no alternative explanation until such time as an informed decision can be made:

- Report an SAE (report term 'Potential Hy's Law') applying serious criteria and causality assessment as per above.
- Continue follow-up and review according to agreed plan. Once the necessary supplementary information is obtained, repeat the review and assessment to determine whether HL criteria are met. Update the SAE report according to the outcome of the review.

Actions required when potential Hy's law criteria are met before and after starting study treatment

This section is applicable to patients who meet PHL criteria on study treatment having previously met PHL criteria at a study visit prior to starting study treatment.

At the first on study treatment occurrence of PHL criteria being, even if there has been no significant change the patient's condition# compared with pre-study treatment visits, the Investigator will:

- Notify the Sponsor representative who will inform the central Study Team.
- Follow the subsequent process described is Section Potential Hy's Law Criteria met of this Appendix.

A 'significant' change in the patient's condition refers to a clinically relevant change in any of the individual liver biochemistry parameters (ALT, AST or total bilirubin) in isolation or in combination, or a clinically relevant change in associated symptoms. The determination of whether

there has been a significant change will be at the discretion of the Investigator, this may be in consultation with the Study Physician if there is any uncertainty.

Actions required for repeat episodes of potential Hy's law

This section is applicable when a patient meets PHL criteria on study treatment and has already met PHL criteria at a previous on study treatment visit.

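### The SAP's liver quadrant counts carry no baseline condition, although eligibility admits patients already above the quadrant lines

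*SAP*

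**What the plan says.** SAP 5.7.2 (Laboratory Data) specifies a quadrant plot in which the "maximum post-baseline ALT or AST (X-axis) and the maximum post-baseline total bilirubin (Y-axis) will be provided". The dividing lines are a "vertical line of ALT or AST equal to 3 x upper limit of normal (ULN") and a "horizontal line of total bilirubin equal to 2 x ULN". It assigns the labels as follows: "The upper right, upper left, and lower right quadrants of the quadrant plot represent the potential Hy's law, cholestasis, and Temple's corollary, respectively". The reported statistic is then: "The number and percentage of participants in the three quadrants will be reported separately". Nothing in this text excludes, flags or separates patients by their baseline values.

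Protocol 4.1, inclusion criterion 8, sets the usual entry ceilings at 2.5 x ULN for ALT/AST and 1.5 x ULN for total bilirubin, with two exceptions. ALT/AST may reach 5 x "ULN if with document hepatic involvement with lymphoma". Bilirubin may reach 3 x ULN with documented Gilbert's syndrome ("unconjugated hyperbilirubinemia) or liver involvement"). Protocol 5.2.2 repeats the higher ceilings for liver involvement.

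Protocol Appendix III defines potential Hy's law by the same two multiples, met on any occasion in the study and not necessarily together. It also has a section for "patients who meet PHL criteria on study treatment having previously met PHL criteria at a study visit prior to starting study treatment".

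**The concern.** The quadrant labels are the language of drug-related liver injury, but the rule behind them looks only at post-baseline values against fixed multiples of ULN. The exceptions in criterion 8 let in patients whose values already lie beyond those lines because of liver lymphoma or Gilbert's syndrome. If their values simply hold steady, they are counted.

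Part B is a single-arm study intended to support a marketing application. No control group shows how many patients would fall in each quadrant from their disease alone. A count that mixes values present at entry with values that arose on treatment is hard to interpret. The label can also mislead: a Gilbert's patient stable at 2.5 x ULN would be tabulated under cholestasis, although the protocol itself describes that condition as unconjugated hyperbilirubinemia.

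**Working it through.** The SAP gives no expected quadrant rate, so there is no plan figure to reproduce. The check compares the cut-offs with the entry ceilings.

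**Step 1. Lines against ceilings (multiples of ULN).**

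| Test | Line (SAP 5.7.2) | Usual ceiling (criterion 8) | Exception ceiling (criterion 8) | Admissible baseline at or above the line |
|---|---|---|---|---|
| ALT/AST | 3 | 2.5 | 5 (hepatic involvement) | 3 to 5 |
| Total bilirubin | 2 | 1.5 | 3 (Gilbert's or liver involvement) | 2 to 3 |

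The usual ceilings lie below the lines, so the problem comes only from patients admitted under an exception. For them both windows are non-empty.

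**Step 2. Where such patients start.**
- ALT/AST 3 to 5, bilirubin below 2: Temple's corollary.
- Bilirubin 2 to 3, ALT/AST below 3: cholestasis.
- Both raised, for example ALT 4 and bilirubin 2.5 with liver involvement: potential Hy's law.

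A patient is counted only if some post-baseline value also reaches the line. Because the rule takes the maximum over all post-baseline values, a stable elevation will meet it. A patient whose values fall below the lines on treatment will not be counted.

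**Step 3. Do other planned outputs separate these patients?**
- By-visit change from baseline and the clinical-significance shift tables (SAP 5.7.2) work one test at a time. They do not show whether a patient in a combined ALT/AST and bilirubin quadrant began there.
- The CTCAE shift tables cannot show a raised baseline for these tests, because SAP 4.3.3 assigns baseline grade 0 to AST, ALT, ALP and total bilirubin.
- Individual listings allow a manual look-up but leave the reported count unchanged.
- Elsewhere the SAP does use baseline: the PR and heart-rate criteria (5.7.3), the LVEF categories (5.7.5) and the DLCO categories (5.7.6) all involve change from baseline.

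**Step 4. Size.** With about 100 treated patients, one patient is 1/100 = 1 percentage point. The documents give neither the share entering above a line (b) nor the share of those with a post-baseline value still above it (q). As an assumption, take b from 1% to 10% and q from 50% to 100%:

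labelled count per 100 = new entries + 100 x b x q

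| b | No new entries, q = 50% to 100% | One new entry, q = 50% to 100% |
|---|---|---|
| 1% | 0.5 to 1 | 1.5 to 2 |
| 3% | 1.5 to 3 | 2.5 to 4 |
| 5% | 2.5 to 5 | 3.5 to 6 |
| 10% | 5 to 10 | 6 to 11 |

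These totals cover the three labelled quadrants together. Restricted to patients below the line at baseline, the count is 0 in the first case and 1 in the second. If no patient enters above a line, there is no effect.

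**The case against.** The strongest reply is that the SAP follows the protocol. Appendix III puts no baseline condition on potential Hy's law, so a quadrant bearing that label is a sensitive screen and not a count of drug-caused cases. That stands, and it is why the unconditioned plot and totals should be kept.

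A reader might infer from the Appendix III section on pre-treatment cases that the SAP contradicts the protocol. It does not. At the first on-treatment occurrence, even without significant change, Appendix III has the investigator notify the sponsor and follow the ordinary process for a potential Hy's law case. Only certain repeat episodes need no action.

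A reader might also infer that new cases would be hidden. For potential Hy's law that goes too far. Appendix III requires the investigator to establish whether the criteria were met before treatment in the presence of liver metastases, to complete liver CRF modules and to join a review of cause. The listings also show baseline values. What remains is that the tabulated count does not carry this information.

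Appendix C of the SAP is not visible. It may hold baseline rules for the separate liver-abnormality table, so one cannot say that the SAP lacks any baseline-conditioned liver summary. SAP 5.7.2 defines the quadrants fully without applying Appendix C to them.

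Finally, the output is descriptive, with no test or decision rule attached, and Protocol 4.3.1 does not regard hepatic disorders as a significant risk for this drug. That limits the weight of the point but does not remove it.

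**Conclusion.** The point holds as a reporting gap. Patients admitted under the criterion 8 exceptions can be counted as potential Hy's law, cholestasis or Temple's corollary with no change on drug, and no visible planned table separates them from new entries to those quadrants. Each adds about 1 percentage point in 100. The total effect is unknown; the ranges above rest on assumed values of b and q and could be zero. Nothing in the documents supports a claim of known inflation, of conflict with Appendix III, or of any effect on the primary ORR analysis. The change is still worth making, because it is cheap and lets a single-arm safety count be read.

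**What to change.** In SAP 5.7.2:

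1. Keep the plot and the total quadrant counts.
2. Add a shift table from baseline quadrant to worst post-baseline quadrant. The simpler alternative is to split each count by baseline status: below both lines, or at or above either line. The shift table is preferable because it also shows a patient who starts with raised ALT/AST and newly crosses the bilirubin line.
3. Give baseline-elevated patients a separate plot symbol.
4. For those patients, show the maximum post-baseline value as a multiple of baseline. Counting only moves between quadrants would miss, for example, ALT rising from 4 x to 15 x ULN with normal bilirubin, which stays in one quadrant.

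The cost is one small table and a plot symbol. Baseline is already defined in SAP 7.1 and the tests are already scheduled before the first dose, so no new data are needed.

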5.7.4 Vital Signs

Vital signs data together with the changes from baseline will be summarized by visit and time point using standard descriptive statistics (mean, standard deviation, median, min and max) in the safety analysis set.

For the vital sign parameters with applicable CTCAE criteria (details are shown in Appendix B), shift tables will be provided to show the shift from baseline CTCAE grade to the worst grade post-baseline.

5.7.5 Echocardiogram/MUGA Scan

The actual value and change from baseline to each visit will be descriptively summarized (mean, median, standard deviation, min, max) for echocardiogram/MUGA scan by visit in the safety analysis set.

The number and percentage of participants with abnormal LVEF decrease (worst case) meeting each criterion below will be reported respectively. Only the post-baseline data will be included for analysis.

- Absolute value $>50\%$
 - Decrease from baseline $\geq 10\%$ and $<20\%$
 - Decrease from baseline $\geq 20\%$
- Absolute value $\geq 40\%$ and $\leq 50\%$
 - Decrease from baseline $\geq 10\%$ and $<20\%$
 - Decrease from baseline $\geq 20\%$
- Absolute value $\geq 20\%$ and $<40\%$
 - Decrease from baseline $\geq 10\%$ and $<20\%$
 - Decrease from baseline $\geq 20\%$
- Absolute value $<20\%$
 - Decrease from baseline $\geq 10\%$ and $<20\%$
 - Decrease from baseline $\geq 20\%$

All the LVEF measurements and change from baseline will be listed in the individual data listing.

